## EQ-5D-5L

Summary score: The percentage at each level can be reported for each of the individual items. The data can be dichotomised into 'no problems' (i.e. level 1) and 'problems' (i.e. levels 2 to 5). The values can be summarised using the UK value set defined below.

EQ-5D-5L value set for England		Example: the value for health state 23245	
constant	1.000	Constant	=1.000
Mobility = 2	0.057	Minus MO level 2	-0.057
Mobility = 3	0.074		
Mobility = 4	0.207		
Mobility = 5	0.255		
Self care = 2	0.059		
Self care = 3	0.083	Minus SC level 3	-0.083
Self care = 4	0.176		
Self care = 5	0.208		
Usual activities = 2	0.048	Minus UA level 2	-0.048
Usual activities = 3	0.067		
Usual activities = 4	0.165		
Usual activities = 5	0.165		
Pain/discomfort = 2	0.059		
Pain/discomfort = 3	0.079		
Pain/discomfort = 4	0.244	Minus PD level 4	-0.244
Pain/discomfort = 5	0.298		
Anxiety/depression = 2	0.072		
Anxiety/depression = 3	0.099		
Anxiety/depression = 4	0.282		
Anxiety/depression = 5	0.282	Minus AD level 5	-0.282
		State 23245	=0.286

## Calculating values: a worked example

Individual scores: The frequency and percentage of patients in each category for the individual items will be reported. The mean and 95% confidence interval for the VAS will be reported.

### Dealing with missing data:

Although the EQ-5D is the preferred measure of HRQoL by several major health technology agencies, including the National Institute for Health and Care Excellence (NICE), the developers of the instrument have not provided recommendations or guidance on how to deal with missing EQ-5D data.

Health economic analysis will not be carried out by the statistician.

Repurposing anti-TNF for treating Dupuytren's disease (funded by Health Innovation Challenge Fund, Wellcome Trust)  
EudraCT Number: 2015-001780-40 and OCTRU Reference Number CTU0028

### 13. APPENDIX 4: ULTRASOUND IMAGES ANALYSIS

At each visit three ultrasound images are taken of the DD nodule being treated; these images are used to guide the treatment of the nodule. Following treatment these images are reviewed by a blinded researcher and the image with the clearest boundaries of the treated nodule is selected to be used for measurement of the nodule size. Using ImageJ the size of each nodule is estimated by calculating the maximal height and Feret of the irregular polygon drawn around the nodule by the researcher who reviewed and selected the images. The area of the nodule can also be estimated using ImageJ software. However, due to the way it is assessed, this measure has been previously identified as both more time consuming and potentially more prone to measurement error than nodule height and feret. Accordingly, nodule area, height and feret will all be summarised descriptively, and height and feret will be explored further using mixed effects regression modelling. Additional explorations of nodule area will be exploratory.

Due to the time consuming nature of the selection of images and the measurement of the nodule size, the secondary outcome analysis will focus on the difference in nodule size between baseline and 12- and 18-months only. If a patient had surgery or withdrew before a time point, then the image from the last available time point will be used.

During blinded analysis of ultrasound images, a review identified that the quality of those from The Netherlands was lower than those from the UK sites. This was due to the different machine being used. Although this allowed for safe injection into the nodule, these images were not suitable for nodule size measurements. The lower resolution of the images resulted in an inability to identify skeletal structures within the hand, which are used to map the nodule and ensure it was assessed consistently over time. Due to this issue, nodule size analysis includes only participants from the UK sites.

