#### **8.8. Discontinuation/Withdrawal of Participants from Trial or Trial Treatment**

Each participant has the right to withdraw from the study treatment at any time. In addition, the investigator may discontinue a participant from the study treatment at any time if the investigator considers it necessary for any reason including:

- Pregnancy
- Significant protocol deviation
- Significant non-compliance with treatment regimen or study requirements
- An adverse event which requires discontinuation of the study medication or results in inability to continue to comply with study procedures
- Hand surgery to remove the nodule being treated.

The reason for withdrawal will be recorded in the CRF. Following withdrawal from study treatment, participants will be encouraged to continue to attend for follow up appointments.

In the event that a participant were to undergo intervention (e.g. surgical excision, PNF, collagenase) to the digit/ray with the treated nodule during the course of the trial, the participant should be encouraged to attend the next follow up appointment. However, physical measures, including tonometry, range of motion and ultrasound assessments are not required (note: hand photograph is required). They should also be encouraged to attend the 12 month follow up appointment so that a blood sample can be obtained. Should the participant have further follow up appointments due (after attending the subsequent and 12 month appointments), or be unwilling to attend for a follow up appointment but agree to complete the questionnaires, the questionnaires may be provided to the participant by email or post for completion. The site must also ensure that any AE or SAE for which reporting is required are identified and submit the relevant CRF(s) as required.

Note: In the event that the participant undergoes surgery to a digit other than the one being treated in the trial, trial treatment and follow up should continue as per protocol.

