### **6.3 Analysis methods: Secondary outcomes**

The secondary analyses will be performed on the ITT population, comparing intervention (adalimumab) against placebo (saline, 0.9% NaCl) for all randomised participants with available data.

Mixed effects regression models will be used to analyse secondary outcomes data, with linear regression for continuous variables and logistic regression for binary variables. Mixed effects regression allows for data from all follow-up time-points to be accounted for, and for adjustment for stratification factors and baseline measurements to be made, where applicable. This procedure is robust and is able to deal with some missing values, either due to missed visits or patients leaving the study prematurely. The time (days) between baseline injection and each follow-up time-point will be included in the models as a random effect to account for patients not all having their follow-up assessments at the same time.

As per the primary outcome, initial analyses for all secondary outcomes will be unadjusted. These analyses will include only outcome measurement and treatment arm, with time since first injection included as a random effect and baseline outcome measurement as a fixed effect. Additional adjusted analyses will be carried out further accounting for centre (Oxford, Edinburgh or Groningen) and age (as a continuous variable). For all models, where appropriate, treatment by time interaction terms will be incorporated to account for changes in effects between treatment arms over follow-up.

Repurposing anti-TNF for treating Dupuytren's disease (funded by Health Innovation Challenge Fund, Wellcome Trust)  
EudraCT Number: 2015-001780-40 and OCTRU Reference Number CTU0028

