#### 6.3.2 Sensitivity analysis

All secondary outcomes will be subject to adjusted mixed effects regression analysis with time not included within the models as a random effect to assess the robustness of the conclusions to the timing of follow-up. The key secondary outcomes, MHQ and range of motion of the treated digit, will have a sensitivity analysis carried out on a PP basis to determine the effect of changes in procedures under which the intervention was received. CACE analysis will also be used to assess data quality and the impact of compliance on these key secondary outcome measures.

For those who have progressed to surgery, an analysis excluding participants where it is not known which digit was operated on will be undertaken.

For sensitivity analyses related to Covid-19, see **Appendix 6: Response to SARS-CoV-2 Pandemic (Covid-19)**.

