## 19.2 Secondary outcomes

**Table 12a:** Mean (with SD) nodule size, as maximal nodule feret and maximal height, recorded at each study time-point

	Saline			Adalimumab			Total					
	N =	n	Mean	SD	N =	n	Mean	SD	N =	n	Mean	SD
Maximal nodule feret												
Baseline												
3 month												
6 month												
9 month												
12 month												
18 month												
Maximal nodule height												
Baseline												
3 month												
6 month												
9 month												
12 month												
18 month												

**Table 10b:** Mean (with SD) nodule area recorded at each study time-point

	Saline			Adalimumab			Total					
	N =	n	Mean	SD	N =	n	Mean	SD	N =	n	Mean	SD
Baseline												
3 month												

Repurposing anti-TNF for treating Dupuytren's disease (funded by Health Innovation Challenge Fund, Wellcome Trust)  
EudraCT Number: 2015-001780-40 and OCTRU Reference Number CTU0028

	Saline			Adalimumab			Total		
	N =			N =			N =		
	n	Mean	SD	n	Mean	SD	n	Mean	SD
6 month									
9 month									
12 month									
18 month									

**Table 13:** Mean (with SD) grip strength recorded at each study time-point

	Saline			Adalimumab			Total		
	N =			N =			N =		
	n	Mean	SD	n	Mean	SD	n	Mean	SD
Baseline									
3 month									
6 month									
9 month									
12 month									
18 month									

**Table 14a:** Mean (with SD) affected digit range of motion active measurements recorded at each study time-point

	Saline			Adalimumab			Total		
	N =			N =			N =		
	n	Mean	SD	n	Mean	SD	n	Mean	SD
MCP – extension									
Baseline									
3 month									
6 month									

Repurposing anti-TNF for treating Dupuytren's disease (funded by Health Innovation Challenge Fund, Wellcome Trust)  
EudraCT Number: 2015-001780-40 and OCTRU Reference Number CTU0028

	Saline			Adalimumab			Total			
	N =	n	Mean	SD	n	Mean	SD	n	Mean	SD
9 month										
12 month										
18 month										
MCP – hyperextension										
Baseline										
3 month										
6 month										
9 month										
12 month										
18 month										
PIP – extension										
Baseline										
3 month										
6 month										
9 month										
12 month										
18 month										
PIP – hyperextension										
Baseline										
3 month										
6 month										
9 month										
12 month										
18 month										

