## 20.2 Secondary outcomes

**Table 20a:** Maximal nodule feret mixed-effects regression results for all follow-up time-points

	Saline N =			Adalimumab N =			Treatment effect N =		
	n	Mean change	SD	n	Mean change	SD	Mean difference	95% confidence interval	P-value
Unadjusted a									
12 months									
Adjusted b									
Baseline									
12 months c									
18 months									

a maximal nodule area and treatment arm | b maximal nodule area, treatment arm, age group and centre | c primary endpoint

Repurposing anti-TNF for treating Dupuytren's disease (funded by Health Innovation Challenge Fund, Wellcome Trust)  
EudraCT Number: 2015-001780-40 and OCTRU Reference Number CTU0028

**Table 18b:** Maximal nodule height mixed-effects regression results for all follow-up time-points

	Saline N =			Adalimumab N =			Treatment effect N =			
	n	Mean change	SD	n	Mean change	SD	Mean difference	95% confidence interval		P- value
Unadjusted a										
12 months										
Adjusted b										
Baseline										
12 months c										
18 months										

a maximal nodule height and treatment arm | b maximal nodule height, treatment arm, age group and centre  
| c primary endpoint

**Table 21:** Grip strength mixed-effects regression results for all follow-up time-points

	Saline N =			Adalimumab N =			Treatment effect N =			
	n	Mean change	SD	n	Mean change	SD	Mean difference	95% confidence interval		P- value
Unadjusted a										
12 months										
Adjusted b										
Baseline										
3 months										
6 months										
9 months										
12 months c										
18 months										

a grip strength and treatment arm | b grip strength, treatment arm, age group and centre | c primary endpoint

Repurposing anti-TNF for treating Dupuytren's disease (funded by Health Innovation Challenge Fund, Wellcome Trust)  
EudraCT Number: 2015-001780-40 and OCTRU Reference Number CTU0028

**Table 22a:** Affected digit range of motion active measurements mixed-effects regression results for all follow-up time-points

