21.2.3 SARS-CoV-2: All secondary outcomes

- (a) Nodule size – maximal feret
- (b) Nodule size – maximal height
- (c) Grip strength
- (d) Range of motion – active measurements
- (e) Range of motion – passive measurements
- (f) MHQ
- (g) Injection pain score
- (h) Progression to surgery
- (i) Most restricted activity

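### On the natural reading, nodule size after surgery or withdrawal is an earlier ultrasound image carried forward to month 12 or 18, with no check on it; separately, imputation of hardness depends on a condition that observed data cannot meet

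*SAP*

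**What the plan says.** **Nodule size.** SAP Appendix 4 states that "the secondary outcome analysis will focus on the difference in nodule size between baseline and 12- and 18-months only". It then gives the rule for participants who leave early: "If a patient had surgery or withdrew before a time point, then the image from the last available time point will be used". It restricts this outcome to the UK sites.

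The result shell in SAP Appendix 5, section 20.2, is titled "Maximal nodule feret mixed-effects regression results for all follow-up time-points", yet its rows are baseline, 12 and 18 months only. The summary shell in section 19.2, "Mean (with SD) nodule size, as maximal nodule feret and maximal height, recorded at each study time-point", also has rows for 3, 6 and 9 months.

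SAP 6.3 analyses secondary outcomes by mixed model, "with time since first injection included as a random effect and baseline outcome measurement as a fixed effect", and says this approach copes with missed visits and early leavers. The planned checks on nodule size are a model "with time not included within the models as a random effect" (SAP 6.3.2) and the pandemic analyses, where "Nodule size – maximal feret" is listed (section 21.2.3). Per-protocol and complier analyses cover only the two key secondary outcomes, the hand questionnaire and range of motion.

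**Why values are missing.** Protocol 8.8 says that after an intervention on the treated digit "physical measures, including tonometry, range of motion and ultrasound assessments are not required".

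**Hardness.** SAP 6.2 analyses 12-month hardness by ANCOVA on participants with data, supported by a mixed model over all visits. SAP 6.2.1 makes chained-equation imputation conditional on MAR being shown to hold. It also plans a pattern-mixture analysis on both imputed and non-imputed data, and leaves the final methods to the blinded analysis. SAP 6.2.2 and output 21.1.5 take an imputed dataset for granted. Output 21.1.3 lists a sensitivity analysis for progression to surgery, but the SAP text gives no method for it.

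**The concern.** With only baseline, 12- and 18-month rows, an earlier image has nowhere to go except into the 12- or 18-month value. A nodule last imaged at month 3 would then count as if seen at month 12, with any later change set to zero. Appendix 4 does not require the image to be post-baseline, so a recorded change of exactly zero is possible. The affected participants are not a random subset, since surgery follows progression. The rule also overrides a model that the SAP says can handle early leavers, and no planned analysis leaves the carried images out.

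For hardness, exploring observed data can give evidence against missingness completely at random, but it cannot separate MAR from missing not at random. Read literally, the condition in 6.2.1 never lets the imputation run, while 6.2.2 and 21.1.5 report it. This matters most for participants operated on before month 12, most of whom leave the primary ANCOVA.

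**Working it through.** **The plan's own figure.** Effect size 0.62, two-sided 5%, 90% power: n = 2 × (1.960 + 1.282)² / 0.62² = 54.7, so 55 per arm. Then 55 / 0.8 = 68.75, so 69 per arm and 138 in total, as stated. The 20% allowance is 0.2 × 138 = 27.6, about 28 participants. The documents give no surgery or withdrawal rate by arm, so all loss rates below are assumed.

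**Carry-forward by hand, month 12.** Let D be the true difference. Assume linear change, and a fraction f in each arm whose last image is at month m. The estimate is D × [1 − f × (1 − m/12)]. If last images are spread evenly over months 0, 3, 6 and 9, the mean m is 4.5:
- f = 10%: 1 − 0.10 × 0.625 = 0.94 of D
- f = 20%: 1 − 0.20 × 0.625 = 0.875 of D

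**Carry-forward by simulation, month 12.** Assumed inputs: 100,000–200,000 per arm; baseline SD 1; true effect −0.50 SD; four correlation structures; placebo/adalimumab growth of 0.5/0 or 1.0/0.5 SD by month 12; change linear to 18 months or flat after 12; surgery after month 0, 3, 6 or 9, with log-odds rising by 1 per SD of the last size.

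| Loss, placebo / adalimumab | Carried forward | Dropped | Own day, baseline as outcome row, slope change at 12 | All 3-, 6-, 9-month images |
|---|---|---|---|---|
| 10% / 10% | −0.464 to −0.479 | −0.492 to −0.505 | −0.495 to −0.507 | −0.495 to −0.506 |
| 20% / 20% | −0.433 to −0.447 | −0.492 to −0.503 | −0.496 to −0.508 | −0.495 to −0.505 |
| 20% / 5% | −0.434 to −0.503 | −0.458 to −0.479 | −0.501 to −0.516 | −0.495 to −0.504 |
| 5% / 20% | −0.421 to −0.501 | −0.519 to −0.540 | −0.483 to −0.500 | −0.495 to −0.505 |

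- Equal loss: the shortfall runs from (0.50 − 0.479)/0.50 = 4% to (0.50 − 0.433)/0.50 = 13%, in line with the hand formula.
- Unequal loss: two forces oppose each other. Growth not seen pulls an arm's mean down; carrying a momentarily large image pushes it up. If every carried image is from month 3 or later, the 20% / 5% range is −0.447 to −0.515, so the effect can be too large as well as too small.
- Dropping these participants is close to unbiased at equal loss but not at unequal loss.
- Own-day entry with baseline only as a covariate and a single straight time line gives −0.451 to −0.552 (20% / 5%) and −0.434 to −0.495 (5% / 20%), no better than carry-forward. This is why the fix keeps baseline as an outcome row.
- If change comes early, own-day entry gives −0.481 to −0.536 and all images −0.488 to −0.503.
- With no true effect and unequal loss, carry-forward is off by −0.019 to +0.017.

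**Month 18, equal loss.** With linear growth carry-forward is about 8–17% too small. If the effect wanes from −0.50 at month 12 to −0.20 at month 18, it gives −0.204 to −0.218 against true values of −0.194 to −0.205, so slightly too large.

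**Scale.** The standard error at 55 per arm is SD × √(1 − ρ²) × √(2/55). In SD units this is 0.17 for ρ = 0.5 and 0.14 for ρ = 0.7. It is larger if fewer UK participants have images.

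**Why MAR cannot be shown.** Shift every unseen hardness value by δ points. The observed data are identical, yet the true difference moves by (missing fraction in one arm − missing fraction in the other) × δ. For δ = 8:
- 25% v 15% missing: 0.10 × 8 = 0.8 points
- 30% v 10%: 0.20 × 8 = 1.6 points
- 20% v 20%: 0

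**Size for hardness** (SD 8, true effect −5, surgery depending on observed hardness). Complete-case ANCOVA gives −4.78 to −5.00 at 10% v 5% surgery, −4.62 to −4.95 at 15% v 5%, and −4.92 to −5.04 at 10% v 10%. Imputation by arm from baseline, 3-, 6- and 9-month hardness gives −4.93 to −5.07. The standard error at 55 per arm is 8 × 0.165 = 1.32 or 8 × 0.136 = 1.09.

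**The case against.** **The reading.** Appendix 4 never says that the earlier image becomes the 12-month value. Since SAP 6.3 puts days since first injection in the model, entry at the true day also fits the text. This stands: carry-forward is the natural reading, given the shells, but not an explicit instruction.

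**The target.** A true effect of −0.50 means nodule size had surgery not occurred. The SAP names no such estimand, and after excision there is no treated nodule to measure. The last size before surgery could be defended as a while-not-operated value. This stands, so the gap is bias only for the no-surgery target.

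**The size.** An equal-loss error of 0.02–0.07 SD sits below a standard error of 0.14–0.17. The outcome is UK-only and not key, and SAP 4.1 treats secondary outcomes as supportive. Under the null the preferred own-day model (−0.017 to +0.014) gains almost nothing over carry-forward. All true, and the reason this is not a major point.

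**What would be visible.** Missing counts with reasons, withdrawals, data availability and surgery by arm are all to be tabulated, and differential loss is tested. These show how many images may be carried and any imbalance, but not the effect on the estimate.

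**The remedy.** A slope change at month 12 is one modelling choice among several, and it suits a path that is flat after month 12. Agreed: what matters is that the form is fixed before data lock.

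**Hardness.** The condition concerns a sensitivity analysis. The pattern-mixture analysis on non-imputed data, the all-visit mixed model and the finalising step at blinded analysis already limit the harm. This stands; what remains is an internal conflict and a missing method for output 21.1.3.

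**Conclusion.** The point holds at modest size. On the natural reading, Appendix 4 carries an earlier image into the 12- or 18-month nodule size, and no planned sensitivity analysis removes it. For the no-surgery, no-withdrawal target with steadily separating arms, the month-12 effect is about 4–13% too small at 10–20% equal loss, and can be off in either direction at unequal loss. These figures rest on assumed loss rates, growth and correlations.

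The condition on MAR in SAP 6.2.1 cannot be met and conflicts with 6.2.2 and output 21.1.5. Complete-case error in the hardness illustration is at most about 0.4 points, against a standard error of 1.1–1.3.

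A reader might infer three stronger claims, none of which is supported:
- That carry-forward always understates the effect. At month 18 a waning effect reverses the direction, even with equal loss.
- That the primary conclusion is at risk. Imputation is not the primary analysis, and departures from MAR are already examined by pattern-mixture modelling.
- That leaving these participants out would cure the problem. It is biased when loss differs between arms.

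**What to change.** **(a) Appendix 4.** Replace the carry-forward sentence:
- The last image before surgery or withdrawal enters the mixed model at its actual day since first injection, with baseline kept as an outcome row, and is never assigned to the 12- or 18-month visit.
- Do not simply drop these participants.
- State the estimand.
- Fix the form of the time trend before data lock; a slope change at month 12 is one option.
- Keep carry-forward only as a labelled sensitivity analysis.
- Reconcile Appendix 4 with the 3-, 6- and 9-month rows in the section 19.2 shell. If those images are measured, use them all in the model, which was the most stable option above.

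**(b) SAP 6.2.1.** Delete the condition and run the chained-equation imputation under an assumed MAR as a sensitivity analysis, by arm, from baseline and earlier hardness, age and centre.

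**(c) Output 21.1.3.** Name the pattern-mixture analysis already planned as its method, with shifts for participants operated on before month 12 fixed before data lock.

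**Cost.** SAP wording and a changed model for one secondary outcome. The primary ANCOVA is untouched and no new data are collected. There will be fewer nominal 12- and 18-month nodule-size values and somewhat wider intervals. Measuring the intermediate images, if chosen, takes reader time that Appendix 4 already describes as substantial.
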